## Specific Aims

This study will employ an innovative and evidence-based digital intervention that includes ten digital assessments (CICADAS app) that will capture data on sensory processing abnormalities and associated cognitive deficits. We will leverage pilot data collected in adolescents with Autism Spectrum Disorder (ASD) and accumulate preliminary evidence for CICADAS app to function as 1) a stand-alone treatment; 2) a primer for PEERS (Program for the Education and Enrichment of Relationship Skills); 3) an enhancer for PEERS. This study will test CICADAS app in adolescents with ASD in a three-arm, active-controlled, randomized crossover trial to document the acceptability and evaluate its potential as a stand-alone treatment, as a primer for PEERS, or as a treatment enhancer of PEERS.

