3) SCT is only available in specialized treatment centers. SCT programs often have a high scheduling burden, requiring multiple weeks of participation and regular in-person clinic visits. This time commitment can be untenable for caregivers who are employed, have other responsibilities to manage, or are without transportation. Additionally, for those who do seek treatment, barriers to receiving it include geographic location, availability of trained therapists, long waiting lists, and the requirement to take time off from school for clinic visits. The remote delivery of SCT through digital devices enables scheduling flexibility and decreases time burden, thus improving accessibility and compliance with intervention requirements, resulting in an increase in cost-effectiveness. In short, digital technology can facilitate access to, and engagement with SCT. In an effort to address these issues and improve outcomes, we propose CICADAS (Care Improving Cognition for ADolescents on the Autism Spectrum)—a digital application that provides an assessment of SPA to tailor the delivery of adaptive, individualized NB-SCT exercises for ASD. By systematically targeting SPA and social cognition deficits, CICADAS app is designed to prime the brain to learn cognitive and relational strategies taught during PEERS groups. We hypothesize that the delivery of the CICADAS app will maximize the impact of PEERS, promoting the generalization of learned skills in the natural environment, and ultimately improving real-world social functioning.

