### Evaluation Time Points

Week 0 –primary and secondary outcome measures are collected on all participants at baseline

Week 16 – primary and secondary outcome measures are collected on all participants

Week 32 – primary and secondary outcome measures are collected on all participants

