**Measures of Social Cognitive Functioning:** We designed CICADAS to improve sensory processing abnormalities and social cognition in adolescents with ASD independently and to work in conjunction with PEERS to further enhance response to treatment. Our rationale is that many individuals are unable to process accurately information that underlies social and interpersonal cues. Thus, improving social cognition via targeted training of sensory processing abnormalities should confer an advantage to participants using CICADAS in conjunction with PEERS. The ability of CICADAS to prime the brain for PEERS will be measured through a subject-specific improvement in social cognition. Social cognitive functioning will be assessed a number of ways in order to gauge gains in social skills as well as ecological validity of the intervention. One of these measures will be the PEERS-based Test of Adolescent Social Skills Knowledge (TASSK; Laugeson & Frankel, 2006), a 22-item survey that assesses the teen's knowledge about the specific social skills taught during the intervention. The TASSK is comprised of sentence stems and two possible answers. Total scores range from 0 to 22, with higher scores reflecting greater knowledge of the taught social skills. Additionally, we will include the performance-based Dynamic Affective Recognition Evaluation (DARE) test for socioemotional abilities in the participant as well as parent-report measures (SRS-2, SSIS-RS) in our outcome a battery.

The secondary statistical analysis methodology is a linear mixed model approach. First, we will investigate in the ITT population any differences in baseline demographic, characterization, outcomes variables. Any such factors that show trend level significant differences ( $p < 0.1$ ) will be noted and used as covariates in the linear mixed model analysis. We will examine the data from each outcome measure using a linear mixed model with group and time as fixed factors, and covariates as necessary from the baseline analysis. Missing data will be handled with an iterative maximum likelihood procedure to optimally estimate model parameters. The key value for significance will be the group by time interaction factor for the model. Within-group effect sizes (Cohen's  $d$ ) will be computed using the mean change scores for quantitative outcomes (end-of-treatment minus baseline) and the change score SDs.

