With 48 participants fully evaluated, we will not have enough power to detect a treatment augmentation effect ascribable to CICADAS. However, data from this pilot trial will be used to power a pivotal RCT in Phase II, as they will allow to explore whether:

- a) the concurrent delivery of CICADAS and PEERS for 16 weeks (B1-B2) induces greater improvements sensory processing, cognition, symptom reduction, social skills and behaviors, as well as quality of life, compared to CICADAS only (A1-A2) or PEERS + Active Control (C1-C2) – *preliminary efficacy of CICADAS as a treatment enhancer for PEERS*;
- b) The concurrent delivery of CICADAS and PEERS for 16 weeks (B1-B2) induces greater improvements sensory processing, cognition, symptom reduction, social skills and behaviors, as well as quality of life, compared to the sequential delivery of CICADAS and PEERS (A1-A3) – *preliminary testing of CICADAS as enhancer vs primer*;
- c) improvements sensory processing, cognition, symptom reduction, social skills and behaviors, and quality of life induced by the concurrent delivery of CICADAS and PEERS (B1-B2) are sustained after 16 weeks of no contact (B2-B3) – *durability of augmentation effects*.

To verify these experimental hypotheses, we will conduct the analysis based on the pre-intervention (baseline) and post-intervention data. The criterion for statistical significance is  $p < 0.05$ . Results with  $p < 0.1$  will be described as trends.

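### The primer role has no pre-specified contrast between PEERS after CICADAS (Arm A, second period) and PEERS without CICADAS (Arm C, first period)

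*SAP*

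**What the plan says.** The protocol (Specific Aims, repeated in General Study Design) will test CICADAS to "evaluate its potential as a stand-alone treatment, as a primer for PEERS, or as a treatment enhancer of PEERS". The Background gives the reasoning: "We hypothesize that the delivery of the CICADAS app will maximize the impact of PEERS". That is a statement about response to PEERS with and without CICADAS.

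The SAP paragraph on measures of social cognitive functioning turns the primer role into a measurement: "The ability of CICADAS to prime the brain for PEERS will be measured through a subject-specific improvement in social cognition". It attaches no comparator and no time window. The measures that follow include the TASSK, which covers "knowledge about the specific social skills taught during the intervention", together with the DARE, SRS-2 and SSIS-RS. Each outcome goes into a linear mixed model with group and time as fixed factors, and the key test is their interaction.

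Three exploratory comparisons are then listed:
- (a) Arm B's first-period change, "compared to CICADAS only (A1-A2) or PEERS + Active Control (C1-C2", for the enhancer role;
- (b) Arm B's first-period change "compared to the sequential delivery of CICADAS and PEERS (A1-A3", for enhancer against primer;
- (c) durability within Arm B.

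All arms are measured at the end: "Week 32 – primary and secondary outcome measures are collected on all participants".

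The documents disagree on Arm A's second period. The protocol (General Study Design, Study Procedures, Treatment Arms) gives it PEERS; the SAP's Statistical Plan gives all three arms no contact. The SAP's ITT population is limited to randomised participants who attended at least one PEERS session.

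**The concern.** Priming means that PEERS works better when CICADAS has come first. A within-person gain in social cognition is a different quantity. It can occur with no change in response to PEERS, and it contains practice and maturation. The one comparison that carries the primer label has CICADAS on both sides. Arm C is the only arm that receives PEERS without CICADAS, and it is not used for this question.

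At stake is one of three stated roles. The SAP says the data will be used to power a Phase II trial, so the quantity estimated for the primer role should be the one a later trial would need.

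**Working it through.** **The plan's own figures.** No figure is given for the primer comparison. The nearest is the sample size: 48 completers, 16 per arm, from 56 recruited at 15% non-completion. 48/(1 − 0.15) = 56.5, or 57 rounded up; 48 × 1.15 = 55.2, or 56. The stated 56 holds to within one participant, and 16 per arm is used below.

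**What each comparison estimates.** Let p be the PEERS gain without CICADAS, c the stand-alone CICADAS gain (assumed to last), k the extra PEERS gain from prior CICADAS (priming), and e the extra gain from concurrent use. Leave practice and maturation aside and follow the protocol's arm descriptions.

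| Change | Content |
|---|---|
| Arm A, V1 to V3 | c |
| Arm A, V3 to V4 | p + k |
| Arm B, V1 to V3 | p + c + e |
| Arm C, V1 to V3 | p |

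- Comparison (a), B against C: c + e. B against A: p + e. Neither contains k.
- Comparison (b): (p + c + e) − (c + p + k) = e − k. It is zero when e = k > 0 (primer as good as enhancer) and when e = k = 0 (CICADAS adds nothing).
- Subtracting (b) from the B-against-C part of (a): (c + e) − (e − k) = c + k. This is A (V1 to V4) minus C (V1 to V3), and it mixes priming with the stand-alone effect.
- A (V3 to V4) minus C (V1 to V3): (p + k) − p = k. The SAP does not name it.

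**Does the general interaction test fill the gap?** A simulation used 16 per arm, 3,000 runs per setting, a 3-group by 3-visit interaction (Wilks test on change scores), unit SD at each visit and between-visit correlation 0.5 or 0.7. CICADAS had no effect. PEERS added an assumed 0.5, 0.8 or 1.0 SD that persisted.
- The interaction test rejected in 26% to 97% of runs, because Arm A receives PEERS one period later.
- A (V3 to V4) minus C (V1 to V3) rejected in about 4% to 5%.
- Comparison (b) rejected in about 5%.

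**A within-person gain.** In Arm A alone (n = 16, paired t, 15 df, noncentrality 4 × d), a practice-only gain of 0.3 SD of change would be significant in 20% of trials, and one of 0.5 SD in 46%. Both gains are assumptions.

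**Precision of the missing contrast.** The half-width of the 95% CI is 1.96 × √(2/16) = 0.69 SD of change, or 2.04 × √(2/16) = 0.72 with t on 30 df. Two-sided power at 5% (sidedness is not stated in the SAP) is 0.28, 0.59 and 0.78 for differences of 0.5, 0.8 and 1.0 SD. The difference detectable with 80% power is about 1.02 SD.

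**Timing at week 32.** Arm A has then just finished PEERS, and Arm C finished 16 weeks earlier. If an assumed 0.6 SD PEERS gain fades by 30%, A gains a false lead of 0.30 × 0.6 = 0.18 SD. If it grows by 30% after PEERS, C gains 0.18 SD.

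**The case against.** Much can be said for the plan. The mixed model contains Arms A and C, so a contrast between them can be derived, and (a) and (b) together imply one. Comparison (b) does use Arm A's outcome after PEERS, on social skills, behaviours and quality of life as well as cognition. Efficacy is secondary, the sample size was set on practical grounds, and the SAP concedes that it lacks power for an augmentation effect.

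These points narrow the concern but do not remove it. The implied contrast is c + k, not priming, and the interaction test responds to the timing of PEERS. Low power argues for estimates with intervals; it does not excuse estimating a different quantity.

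A reader might go further than the documents allow:
- *Any gain in social cognition would count as proof of priming.* The SAP sets no threshold or yes/no rule, and a practice gain equal across arms does not produce an interaction.
- *Arms A and C are never compared.* They are in the same model; what is missing is a named contrast.
- *An A minus C difference must favour A.* At week 32 that depends on PEERS gains fading. Over the PEERS period, Arm C also has an app designed to match expectation, while Arm A has PEERS alone. If practice gains are largest at the first retest, that too favours C.
- *Phase II would adopt sequential delivery on this basis.* The documents do not say so.

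**Conclusion.** The concern stands in limited form. The SAP defines the primer role as a within-person gain in social cognition, and its only comparison labelled primer has CICADAS in both arms. No pre-specified contrast isolates whether PEERS works better after CICADAS than without it. Comparison (b) cannot tell equal primer and enhancer effects from no CICADAS effect, and adding (a) recovers only the sum of priming and the stand-alone gain.

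The contrast that isolates response to PEERS can be formed from scheduled visits, but only to about ±0.7 SD of change at 16 per arm. It also compares different calendar periods and test exposures, and the control app accompanies PEERS in Arm C only. The direction of bias is uncertain, so the design can explore priming but not establish it.

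This rests on Arm A receiving PEERS in its second period. Under the SAP's no-contact wording there would be no PEERS period after CICADAS to analyse, and comparison (b)'s sequential delivery would not exist either. The effect sizes, correlations and fade used above are assumptions; the documents give none. The primary feasibility outcomes are not affected.

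**What to change.** First reconcile Arm A's second period between the SAP's Statistical Plan and the protocol's General Study Design, Study Procedures and Treatment Arms. Then, if Arm A has a PEERS period there, replace the SAP sentence on priming with text such as:

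> Change in social cognition from V1 to V3 is reported as target engagement and compared between arms. Priming is explored by two estimates with 95% CIs, on social skills and functioning: (i) the gain over the PEERS period, Arm A (V3 to V4) minus Arm C (V1 to V3); (ii) as support, the baseline-adjusted Arm A minus Arm C difference at week 32, which also contains any stand-alone CICADAS effect. The arms differ in calendar period, in number of test exposures, in time since PEERS at week 32, and in the control app given with PEERS in Arm C. The direction of bias is uncertain.

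For target engagement, B minus C is the cleaner comparison, since A and C also differ in PEERS; this matters most for the TASSK.

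Keep all randomised participants in these estimates. Under the ITT rule Arm A can qualify only in the second period, so its early leavers would drop out of the comparison while Arm C's could stay in.

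In Specific Aims and General Study Design, say that the trial explores the primer role. The cost is wording and two estimates; no visit or measure is added, and one objective is stated more modestly.

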| Emotional Face  | Emotional Conflict Resolution        | Gaze Match            | Gaze matching task           |
|   |                                      | To-do List Training   | Verbal working memory task   |
|   |                                      | In the Know           | Auditory social memory task  |
|   |                                      | Auditory Ace          | Auditory working memory task |
| *using emotionally expressive faces and emotional valence words |                                      |                       |                              |

**Active Control app:** Participants will play previously-vetted and popular casual video games for an overall duration that is time-matched to the CICADAS program. These games are designed to *not* actively engage the neural systems that underlie ASD. With this kind of control, the current study will be able to assess convergent validity (i.e., that exercises that should improve cognitive function, in fact do) and discriminant validity (that exercises that should not improve cognitive function, in fact don't). We will use control games that are designed to be a face-valid approach to cognitive training, that can be described to participants as a valid approach for improving brain health, and that support a matching of the

expectation-based influence on performance in neuropsychological outcome measures. Participants will also complete the sensory processing assessments before and after the first intervention period.

We will carefully match the CICADAS program and the active control program in overall program use intensity, modality (visual), mode of delivery (supervisor portal), time-spent attending, delivery of rewards, and overall engagement; and provide a comparison group that matches the CICADAS group on the aforementioned attributes, but without the key elements specific to improving the neuro-modulatory control of the brain. Variety and novelty are critical to maintaining participant engagement in the active control group. Here are some examples of the games below:

- Lineup Four: Line up four chips in a row before your opponent.
- Bricks Squasher II: Move a paddle and bounce the ball to destroy the bricks.
- Gems Swap: Form a line of 3 or more identical gems by swapping their positions.

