## Sample Size Justification

Attrition rates from the ASD pilot study conducted at University of Minnesota were > 30%. This high dropout rate can be ascribed to design issues, in that: (1) the sample recruited for the pilot consisted of adolescents who were not intrinsically interested in long-term treatment options for ASD, unlike the current target (adolescents already seeking PEERS); and (2) study coordinators had not been formally trained on how to keep participants engaged in a remote cognitive training intervention. By recruiting adolescents already seeking PEERS and by rigorously training our staff, we expect retention rate for this project to be in line with those of 1) cognitive interventions delivered to adolescents with ASD; 2) PEERS groups. We project a 15% non-completion rate estimate for this study. We will recruit 56 participants to obtain 48 study completers. As the primary aim of this study is to gather information about the feasibility, acceptability and usability of this approach, the sample size of N=56 is set primarily for practical reasons and not driven by hypothesis testing. This size will, however, provide data to power a subsequent pivotal efficacy trial in Phase II, and will provide the field validation data required to submit CICADAS to the FDA as a medical device for such a trial

under the 510k de novo process. We are confident that we will meet our recruitment goals with these resources in place.

Of interest to the design of our proposed trial, despite randomization to the auditory or visual training conditions, 73.2% of participants who were assigned to the Visual condition at BL completed the training whereas only 38.5% of participants who were assigned the Auditory Condition completed the program. This highlights the importance of personalized intervention programs that take individual differences (e.g., auditory sensitivity) into consideration. In fact, several participants who chose to discontinue attributed their decision to an aversion to the auditory stimuli used in the computer programs. Baseline SCAN Competing Words Test scores were significantly related to whether individuals randomized to the Auditory or Visual NB-SCT Modules completed their training [ $F(2,23) = 6.331, p = .006$ ]. In other words, participants randomized to the Auditory NB-SCT who did not complete their program had significantly more auditory processing difficulties than those who completed the program.

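### The p<0.1 covariate screen would usually leave baseline SCAN Competing Words, the pilot's documented predictor of non-completion, out of the likelihood model that handles missing data

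*SAP*

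**What the plan says.** **Missing data and covariates.** The SAP (statistical methodology under Measures of Social Cognitive Functioning) plans a linear mixed model with group and time as fixed factors, judged on the group-by-time interaction. "Missing data will be handled with an iterative maximum likelihood procedure". Baseline variables are first compared between arms. "Any such factors that show trend level significant differences" (p<0.1) become covariates. Neither baseline SCAN-3 nor the sensory-symptom randomization stratum (SAP, Statistical Plan) is a prespecified model term, and no sensitivity analysis for missing data is given.

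**Pilot evidence.** The Protocol (Sample Size Justification) gives a completion rate of 73.2% for visual training. For auditory training the rate was far lower: "only 38.5% of participants who were assigned the Auditory Condition completed the program". Baseline SCAN Competing Words was related to completion, "F(2,23) = 6.331, p = .006". The Protocol explains that "participants randomized to the Auditory NB-SCT who did not complete their program had significantly more auditory processing difficulties than those who completed the program". Several participants who stopped cited aversion to the auditory stimuli.

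**This trial.** SCAN-3 is scheduled for everyone at V1, V3 and V4 (Protocol, Appendix I). The CICADAS app used in Arms A and B includes auditory and prosody exercises (Protocol, Treatment Interventions). The Protocol projects 15% non-completion.

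**The concern.** Maximum likelihood with incomplete outcomes gives unbiased estimates only if missingness is random given what the model contains. If a variable drives both dropout and outcome change, and does so unequally between arms, leaving it out moves the group-by-time estimate away from the truth.

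The sponsor has evidence on one such candidate and collects it at baseline, but the plan does not use it by design. Whether it enters depends on a significance test of chance imbalance between randomized arms. That test carries no information about who drops out. A well-balanced score can still be the reason participants leave one arm.

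At stake is the comparison of PEERS + CICADAS (B) with PEERS + Active Control (C), which is evidence for CICADAS as an enhancer of PEERS. The SAP concedes low power for this comparison but says the data will be used to power the Phase II trial.

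**Working it through.** **1. The pilot test.** The upper tail of F(2,23) at 6.331 is p = 0.0064, matching the stated .006. The degrees of freedom imply 2 + 23 + 1 = 26 participants. Eta-squared = (2 × 6.331)/(2 × 6.331 + 23) = 12.662/35.662 = 0.36.

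**2. The completion contrast.** Non-completion is 100 − 38.5 = 61.5% (auditory) and 100 − 73.2 = 26.8% (visual). No denominators or test are given. The smallest group that yields 73.2% is 30/41, which cannot be a subset of the 26 participants in step 1. Fisher's exact p would be 0.04 for 5/13 versus 30/41, but 0.11 to 0.24 with 13 per arm (5/13 versus 10/13 or 9/13). This part is descriptive; the SCAN result is the firm part.

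**3. How often the screen admits SCAN.** Under simple randomization any baseline score passes a p<0.1 test about 10% of the time (simulated with 57 participants in three arms: 10.6%). If the sensory stratum is a two-level split correlated 0.3, 0.5 or 0.7 with SCAN (assumed), the rate falls to about 8%, 7% or 4%. SCAN is left out roughly 90-96% of the time.

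**4. Size of the bias.** Assumptions, none of them in the documents:
- S is the standardized baseline SCAN score (higher is better).
- Outcome change = ρS + error, with SD 1 and no true treatment effect.
- Arm B: logit P(missing) = a − 1.5 S, with a set to give the stated loss.
- Arm C: missingness is unrelated to S.
- S is uncorrelated with the baseline outcome.

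In large samples, omitting S then gives

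bias in group × time = ρ × E[S | observed, Arm B].

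Numerical integration over a standard normal S gives:

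| Loss in Arm B | a | E[S given observed] | ρ = 0.1 | ρ = 0.3 | ρ = 0.5 |
|---|---|---|---|---|---|
| 15% | −2.37 | 0.175 | 0.02 | 0.05 | 0.09 |
| 30% | −1.19 | 0.327 | 0.03 | 0.10 | 0.16 |
| 61.5% | 0.66 | 0.658 | 0.07 | 0.20 | 0.33 |

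Fitting a two-arm, two-visit maximum likelihood model to simulated data, with Arm C loss of 15%, 15% and 26.8% respectively, agrees within simulation error of about 0.02. This also holds when S correlates 0.3 with the baseline outcome.

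**5. Which model term removes it.** From the same simulations at 30% versus 15% loss and ρ = 0.3:

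| Correlation of S with baseline outcome | SCAN omitted | SCAN additive only | SCAN × time |
|---|---|---|---|
| 0 | 0.097 | 0.097 | 0.000 |
| 0.3 | 0.095 | 0.103 | 0.004 |

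An additive term shifts all visits equally, so it cannot correct a bias in change.

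**6. Bias against noise.** With about 19 randomized per arm (56/3) and 15% loss, about 16 per arm remain. The standard error of B − C is about √(2/16) = 0.35 SD, so a bias of 0.09 is about a quarter of it (0.09/0.35). Simulated root mean squared error, SCAN omitted versus adjusted, at 15% loss in both arms:
- ρ = 0.1: 0.357 versus 0.363
- ρ = 0.2: 0.356 versus 0.354
- ρ = 0.3: 0.358 versus 0.347
- ρ = 0.5: 0.360 versus 0.312

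**The case against.** **Stopping the app is not missing the assessment.** The pilot figures concern completing the training. Here participants may stop using the program and still attend V3 or V4 (Protocol, Description of Protocol Devices), and those withdrawing for lack of time are offered the end-of-study visit (Protocol, Withdrawal from the Protocol). The bar is low: 1 hour of NB-SCT plus, in Arm B, one PEERS session (SAP, Primary Outcome - Feasibility). This largely stands. It is not complete protection: assessment is conditional on meeting that minimum, and the Protocol expects some participants to withdraw outright.

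**The pilot arms are not B and C.** The pilot compared auditory with visual modules. CICADAS mixes modalities and personalizes delivery, and by name or task label about 4 of its 13 exercises are auditory or prosodic. The Protocol lists visual modality among the attributes on which the two apps are to be matched. This stands. A reader might infer that 61.5% against 26.8% loss, and hence a bias of up to 0.33 SD, applies to B versus C. The documents do not support that: the rates come from single-modality training, have no denominators or test, and are not rates of missing outcomes.

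**The size rests on assumptions, and the analyses are exploratory.** Both are true. No document gives the correlation of SCAN with outcome change or the slope of dropout on SCAN. At the projected 15% loss the bias is small beside sampling error, and adjustment clearly helps only if SCAN is fairly prognostic. What remains is that the screen is the wrong tool for choosing a covariate that supports a missing-data assumption, and that the better choice costs almost nothing.

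**Conclusion.** The point holds as a weakness in how covariates are chosen, not as a demonstrated bias. The pilot reports one measured baseline predictor of non-completion, and the plan would omit it about 90% of the time or more, because its rule tests imbalance between arms and not dropout.

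Bias in B versus C follows only if all three conditions hold: stopping the app produces missing V3/V4 outcomes, that missingness depends on SCAN more strongly in the CICADAS arms than in control, and SCAN predicts outcome change. Under the stated assumptions it is about 0.02-0.09 SD at the projected 15% loss and 0.03-0.16 SD at 30% versus 15%. The pilot rates give only an upper bound. The direction is unknown: it would favor CICADAS if better auditory processing goes with larger gains, and disfavor it if the reverse.

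It would go too far to say that participants with poor auditory processing will leave the CICADAS arms more often. The pilot makes this plausible; this trial's design and retention plan may prevent it. A change to the SAP is still worthwhile because the estimates are meant to inform Phase II and the score is already collected.

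**What to change.** In the SAP's mixed-model paragraph:

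- Prespecify the baseline SCAN-3 Competing Words score (the subtest the pilot identified) and its interaction with time as fixed terms in the outcome models, regardless of the p<0.1 screen. An additive term alone is not enough.
- Except models where SCAN-3, or the Cognition composite that contains it (SAP, Calculations from CRFs), is the response. Otherwise the same baseline score would be both response and covariate.
- Report training completion and, separately, missing V3 and V4 assessments by arm and baseline SCAN. This shows whether stopping the app does lead to missing outcomes.

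**Cost.** A short SAP amendment and no new data. With three visits treated as categories, the model gains up to three parameters (one main effect, two interactions). If SCAN is only weakly prognostic the precision loss is negligible: root mean squared error rises by about 0.006 SD at a correlation of 0.1, and falls at 0.3 and above.

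**Limit.** The within-group Cohen's d in the same section uses raw change scores, so this covariate does not protect it. Those values should be read alongside the completion table.
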